3 OBJECTIVES AND ENDPOINTS

| OBJECTIVES | ENDPOINTS | JUSTIFICATION FOR ENDPOINTS |
|---|--|--|
| Primary | | |
| Determine the effect of automated medication adherence platform (HiDO) on medication compliance. | Mean adherence rate to ART in all patients across 90 days (quantified as (n. of doses provided — n. of doses taken) / n. of doses provided x 100) | Adherence data are automatically and continuously recorded by HiDO device, and directly confirmable through manual audit of video recordings. |
| Secondary | | |
| Determine usability of automated medication adherence platform (HiDO), as indicated by user ease of adoption (Time on Task, error rates), standardized user experience metric (SUS), and user endorsement (Net Promoter Score). | 
Measured at Week 2:
 
 • Time on Task for initial registration • Time on Task for “first click” testing • Time on Task for facial recognition setup • Time on Task for medication administration • Number and type of critical and non-critical errors • Error-free rate 
Measured after 90 days use of platform:
 
 • Score on System Usability Scale (SUS) • Net Promoter Score | 
Time on Task and error rates may be compared to published benchmarks for similar platforms.
 
According to usability.gov published by the U.S. Department of Health & Human Services, the SUS is regarded as a reliable tool to assess usability and has become the industry standard.²⁴ Results from the SUS have been published in over 1,300 publications.²⁴ It can be used on small sample sizes with reliable results and can effectively discriminate between usable and unusable systems.
 
The Net Promoter Score is based on the response to the question, “How likely is it that you would recommend our device to a friend or colleague?” on a 5-point Likert scale.
 |

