| Description of Study Intervention: | HiDO is an automated Artificial Intelligence driven direct observation medication adherence platform. The platform is a 510K exempt Class I medical device (890.5050) that integrates medication dispensing, dose administration time, pill count and front facing video cameras to validate the right medications, at the right time to the right patient. The device dispenses up to 7 different types of medications simultaneously. The camera logs every dose using facial recognition and provides real time consumption logs. Investigators have access to video observation logs, patient dose time, adherence trends, and study level adherence measures. For this study, the HiDO medication adherence platform will be delivered to the residence of each participant by the researcher, who will provide instructions for performing device setup that includes linking the HiDO device to the participant’s smartphone and filling the device with ART. The participant receives a smartphone alert when it is time to take a medication, and then pushes the button on the device to receive the correct medicine at the given time. If the patient does not respond, additional reminders are sent via phone and SMS. Medication adherence will be measured over 90 days using the HiDO device. Additionally, participants will participate in a semi-structured interview following the 90-day period to assess system usability. |
| Study Duration: | 12 months |
| Participant Duration: | 104 days |

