HiDO is the first device of its kind to integrate medication reminders, patient reported outcomes, drug dispensing, and remote/recorded observed therapy in a single platform (see Figure 2). The device collects real-time data for medication adherence, dose administration time, 14-day adherence trend analysis and video recording of medication consumption. These capabilities help satisfy the new FDA remote-monitoring guidance issued August 2020. Both pharmaceutical and clinical trial organizations have expressed interest in leveraging the HiDO device across the HIV and other drug development pipelines. While clinical trialists do use body fluid sampling to assess adherence, the advent of COVID-19 has dramatically reduced in-person clinical trial visits. Sponsors are aggressively pursuing ways to meet FDA requirements with fewer in-person visits.

Figure 2. Comparison of HiDO with available medication adherence platforms.

| Product | Description | Pros | Cons |
|---------|---|---|--|
| HiDO | Automated video-observed therapy and medication dispenser | 
 Sorts and dispenses pills Observes and records therapy Facial recognition biometrics Tracks drug administration Medication reminders Holds up to 7 drugs x 40 doses Can be used with standard pill bottle | 
 Some patients may not like video recording |
| Proteus | Ingestible sensor | 
 Completely assures drug is swallowed | 
 Patients don't like swallowing a device Patients must track their own medications and regimen No integrated reminders FDA approval required for each molecule (very costly) |
| AiCure | Video-observed therapy via smartphone | 
 Observes and records therapy Facial recognition biometrics | 
 Patients must be able to hold the phone properly to engage the device Cumbersome and tedious Some patients may not like video recording |
| Livi | Medication dispenser | 
 Sorts and dispenses pills Tracks drug administration | 
 Does not observe therapy Uncontrolled ejection of pills or pills get stuck Large, bulky unit Does not detect pills Not a "smart" unit High user burden |

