 - Patient Profile describes key components of a patient in an easy-to-use structure in four categories delineated by tab structures including: General, Insurance, Personal, and Clinical information for that patient; the goal is to minimize the information stored on this profile to be only the patient information needed to assign surveys (e.g., demographic, disease or condition, insurance type), assist the clinician in the clinician survey process, and provide a database suitable to support research and clinical studies; ideally, the information that is contained on the clinicians electronic medical record (EMR) is downloaded from that system and not re-entered

Video/Audio recording of the medication consumption is about 10 seconds in duration. The recording does not start until the patient unlocks the device with facial recognition and verifies the appropriate medication dispensing. The research team is HIPPA certified, and recordings are encrypted via AWS secured HIPPA storage.

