6.1.2 DOSING AND ADMINISTRATION

The Principal Investigator will deliver the device to the participant's home and will assist each participant with initial device setup that includes filling the device with ART (the device holds and can dispense up to 7 different medications), installing the device app on the participant's smartphone, and configuring the device and app. The participant receives a smartphone alert when it is time to take a medication. The participant then pushes the button on the device and receives the correct medicine at the given time. In addition to tracking time, frequency, and other medication administration data, the

device video records the interaction to verify that the medication was consumed. If the patient does not respond, additional reminders are sent via SMS and read as: "It's time to take your morning medication" (for late doses scheduled for 12pm Pacific Time or earlier) or "It's time to take your evening medication" (for late doses scheduled after 12pm Pacific Time).

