7 STUDY INTERVENTION DISCONTINUATION AND PARTICIPANT DISCONTINUATION/WITHDRAWAL

7.1 DISCONTINUATION OF STUDY INTERVENTION

Discontinuation from HiDO platform use does not mean discontinuation from the study, and remaining study procedures should be completed as indicated by the study protocol. Although not expected to occur, if a clinically significant finding is identified after enrollment, the investigator or qualified designee will determine if any change in participant management is needed. Any new clinically relevant finding will be reported as an adverse event (AE).

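### The primary adherence rate divides by an undefined number of doses provided; on the protocol's own dosing steps, that number would leave out ignored alerts

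*Combined protocol and SAP*

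**What the plan says.** Section 3 labels the primary endpoint "Mean adherence rate to ART in all patients across 90 days" and ends its formula with "n. of doses taken) / n. of doses provided x 100". The numerator as printed is doses provided minus doses taken. The word *provided* is not defined anywhere.

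Two places describe dosing step by step, and they agree. In Section 1.1 the participant receives an alert "and then pushes the button on the device to receive the correct medicine at the given time". Section 6.1.2 says: "The participant then pushes the button on the device and receives the correct medicine at the given time". For silence, it says: "If the patient does not respond, additional reminders are sent via SMS". Neither section says that an unanswered alert is logged as a missed dose or stays in the denominator.

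Other text points towards a schedule:
- Section 2.2 describes the unit dispensing at a set time and dose, with no button mentioned.
- Section 2.3.3 refers to a failure of automatic dispensing.
- Section 4.2 limits the calculation, for complete withdrawals, to the time they took part.
- Section 6.1.1 lists missed as well as taken pills among the dashboard contents.
- Section 6.1.2 words its reminders around late scheduled doses.

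Two further facts bear on the count. Section 7.1 states: "Discontinuation from HiDO platform use does not mean discontinuation from the study". Sections 2.2 and 2.3.3 let participants take medication out of the unit by hand.

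**The concern.** Not responding to the alert is an obvious way to miss a dose under this system. Missed doses are to be expected, because Section 5.1 requires self-reported intake below 100% in the past 30 days. If *provided* means dispensed after a button press, an unanswered alert enters neither part of the ratio. The endpoint then measures how many requested doses were swallowed, not how many prescribed doses were taken.

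The video audit that Section 3 offers as confirmation would not reveal the gap. Section 6.1.1 says: "The recording does not start until the patient unlocks the device with facial recognition and verifies the appropriate medication dispensing". An ignored alert therefore leaves no video to audit.

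Section 9.4.2 judges the hypothesis by descriptive statistics alone, so the choice of denominator can decide whether the ≥95% goal is declared met.

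**Working it through.** The plan gives no worked value of the endpoint, so there is no figure of its own to reproduce on this point.

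**Inputs from the documents:** success threshold ≥95% over 90 days (Sections 4.1 and 9.1); assumed baseline adherence 54% to 68% (Section 9.2).

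**Assumptions:** one dose per day, so S = 90 scheduled doses; taken over provided as the intended ratio; no manually retrieved doses. The figures are for one participant, or for a group who all behave alike.

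**Step 1: the two readings.** Let I be ignored alerts and U doses dispensed but not swallowed. Doses taken are S − I − U.
- Provided = dispensed: (S − I − U) / (S − I)
- Provided = scheduled: (S − I − U) / S

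| I | U | Dispensed reading | Scheduled reading |
|---|---|---|---|
| 20 | 1 | 69/70 = 98.6% | 69/90 = 76.7% |
| 9 | 4 | 77/81 = 95.1% | 77/90 = 85.6% |
| 5 | 0 | 85/85 = 100% | 85/90 = 94.4% |

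In all three rows the dispensed reading meets 95% and the scheduled reading does not.

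**Step 2: dependence on the type of miss.** Let a be true adherence to the schedule and s the share of misses that are ignored alerts. The dispensed reading is a / (1 − s(1 − a)). The documents do not give s, so a range is shown.

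| True a | s = 0 | s = 0.5 | s = 0.9 | s = 1 |
|---|---|---|---|---|
| 54% | 54.0% | 70.1% | 92.2% | 100% |
| 68% | 68.0% | 81.0% | 95.5% | 100% |
| 80% | 80.0% | 88.9% | 97.6% | 100% |

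For example, 0.68 / (1 − 0.9 × 0.32) = 0.68 / 0.712 = 95.5%.

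**Step 3: share needed to cross the bar.** Setting the expression to 0.95 gives s = (1 − a/0.95) / (1 − a). For a = 0.90 this is 0.0526 / 0.10 = 53%.

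| True a | Share of misses that must be ignored alerts |
|---|---|
| 54% | 94% |
| 68% | 89% |
| 80% | 79% |
| 90% | 53% |
| 94% | 17.5% |

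**Step 4: the formula as printed.** With provided minus taken on top, the first example gives (70 − 69)/70 = 1.4% or (90 − 69)/90 = 23.3%. These are non-adherence rates and cannot be compared with ≥95%. Turning the numerator round is necessary, but the denominator would still be open.

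**The case against.** The best defence is that the protocol may intend a schedule-based count throughout. The withdrawal rule in Section 4.2 is hardly needed if the denominator is button presses, since withdrawal would cut that count off by itself. A missed pill on the dashboard has meaning only against a schedule, and reminders for late doses show that the device knows what is due. Section 8.2 expects the logs to reveal adherence well below baseline, which would be hard if ignored alerts vanished. This stands as far as it goes: the schedule-based reading is available and carries no such bias. But no section ties the endpoint to it, and the two step-by-step descriptions point the other way.

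A reader might infer more than the documents support:
- *That the plan definitely counts only button presses.* This is an inference. The term is undefined, and the descriptions of dispensing do not agree with each other.
- *That the 95% goal would be met whatever the true adherence.* Doses dispensed but not swallowed still count as missed. At true adherence of 68%, about 89% of misses would have to be ignored alerts.
- *That a participant who stops pressing on Day 31 but stays in the study scores 30/30.* This follows only on the dispensed reading. Section 4.2 shortens the count only for complete withdrawal, which suggests that others are counted throughout.
- *That reading provided as loaded gives a perfect user 90/120 = 75%.* This needs three full fills. Figure 2 in Section 2.2 states only a capacity, "Holds up to 7 drugs x 40 doses"; no section says how much is loaded.

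The timing of the video in Section 6.1.1 limits what can be audited. It does not define what enters the dose log.

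**Conclusion.** The denominator of the sole primary endpoint is undefined. On the dosing steps in Sections 1.1 and 6.1.2, ignored alerts fall out of it; on other text they stay in. Two analysts could follow the protocol and report 98.6% and 76.7% from the same participant's log.

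The size of the bias is not known. It runs from zero, if provided means scheduled or no misses are ignored alerts, up to the whole of the missed share if all of them are. It matters most for participants a little below the goal: at true adherence of 94%, 17.5% of misses being ignored alerts is enough to reach 95%. The figures rest on once-daily dosing where counts are used, on taken over provided as the intended ratio, and on no manual retrieval.

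The ambiguity is certain. That the trial would actually count only dispensed doses is not. The definition should be settled before the data are analysed.

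**What to change.** In Section 3, together with correcting the inverted numerator, define each participant's adherence as scheduled ART doses confirmed taken, divided by ART doses scheduled under the prescribed regimen over that participant's observation window, × 100. Specify that:
- The window is Day 1 to Day 90, or to the documented date of withdrawal or discontinuation from the study for any reason covered by Sections 4.2, 7.2 and 7.3.
- Unanswered alerts count as not taken.
- Days after device use stops stay in the denominator while the participant remains in the study (Section 7.1).
- Doses retrieved by hand or affected by device malfunction (Sections 2.2 and 2.3.3) are counted and reported separately, with a sensitivity analysis scoring them first as taken and then as not taken.

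The descriptions of dispensing in Sections 1.1 and 6.1.2 and those in Sections 2.2 and 2.3.3 should also be reconciled.

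The cost is a few sentences and a different count from logs already collected; the reminder and dashboard functions suggest that the device holds the schedule. The downside is that reported adherence may be lower, and that unobserved manual doses may be under-credited in the main count. The sensitivity analysis would show by how much, for the manual doses that can be identified.

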4 STUDY DESIGN

4.1 OVERALL DESIGN

Study description: This is an unblinded, Phase 1 study of the HiDO automated medication adherence platform in patients ages 18 and older with HIV/AIDS who are currently taking ART. For this single-site device study, clinical collaborators will recruit 24 participants into a single study group. After a screening period of up to 14 days, participants will receive the 90-day intervention that consists of using of an automated medication adherence platform. Medication adherence will be assessed through observed therapy using front-facing cameras on the device.

Study device: HiDO is an automated Artificial Intelligence driven direct observation medication adherence platform. The platform is a 510K exempt Class I medical device that integrates medication dispensing, dose administration time, pill count and a front facing video camera to validate the right medications, at right time to the right patient. The camera logs every dose using facial recognition and provides real time consumption logs. The device dispenses up to 7 different types of medications simultaneously. Investigators have access to video observation logs, patient dose time, adherence trends, and study level adherence through a cloud-based electronic dashboard. Data is stored securely in the cloud and accessible real-time.

Study Procedures: As part of screening procedures, participants complete a 10-minute medication adherence self-assessment via phone. The researcher will schedule a visit to the participant's home, expected to last approximately 45 minutes, to conduct consent process and set up the device. After conducting consent procedures and collecting participant demographic information, the researcher will deliver the HiDO device to each participant's home and assist each participant with platform setup, which includes loading ART medications into the dispenser (up to 7 different types), calibrating facial-recognition, and setting up the participant's smartphone to interact with the device. Following platform setup, participants use the HiDO platform for 90 days, which will provide notifications for, dispense, and monitor each participant's ART dosing. At the end of the 90-day intervention period, participants complete a semi-structured interview, administered via phone and lasting approximately 30 minutes, to assess device usability and complete post-intervention medication adherence self-assessment. Excluding screening, total study duration is 104 days +/- 7 days.

Data are collected for medication adherence and usability from the following sources:

1. Medication adherence:
 - a. Automated dosage logs generated by HiDO device
 - b. Manual audit of automated dosage logs
 - c. Pre- and post-study medication adherence self-assessment questionnaire
2. Usability:
 - a. Automated user logs generated by HiDO device
 - b. Post-study semi-structured interview
 - c. System Usability Scale
 - d. Net Promoter Score

Hypotheses:

Hypothesis 1: Use of the HiDO automated medication adherence platform will result in ≥95% medication adherence over 90 days.

Hypothesis 2: Usability scores for the HiDO platform (as measured by Time on Task for initial registration, “first click” testing, facial recognition setup, and medication administration, number and type of critical and non-critical errors, and error-free rate) will be equal to or better than published benchmark rates for similar platforms.

Hypothesis 3: The System Usability Scale (SUS) value for the HiDO platform will be equal to or better than published benchmark rates for similar platforms (>68).

Hypothesis 4: Greater than 80% of participants will indicate that they are Likely or Strongly Likely to recommend the HiDO device to a friend or colleague.

Selection bias: Every effort will be made to draw a sample that represents the patient population in terms of race, ethnicity, and gender.

4.2 SCIENTIFIC RATIONALE FOR STUDY DESIGN

Our main goal is to demonstrate $\geq 95\%$ adherence to ART in all patients across 90 days. Admittedly, this is a very high bar. However, we are confident that we will achieve it, even for patients who have problematic use. Our informal user testing to date has shown remarkable adherence rates with the HiDO device, and these have improved as we have moved into the current version (Version 3).

For participants who completely withdraw from the study before 90 days, adherence percentage will only be calculated for the time that they participated. While we will likely glean important information from those who do drop out early, these dropouts will not affect our primary endpoint calculation. We may also fail to recruit a pool of participants that reflects the diversity of the national HIV patient population. We expect, however, to be close, and will be able to recruit a sample sufficient to intelligently plan for larger scale future testing in diverse populations. If successful, we will have demonstrated that our automated medication adherence platform is highly usable, preliminarily enables strict adherence to ART, and is ready for larger scale testing in Phase II.

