Efforts to improve adherence are only modestly successful. Multiple factors contribute to nonadherence.¹⁴ These factors include the complexity of taking medications, time burden on the patient, the patient's perception of benefits and risks. Several measures have been proposed and deployed to improve adherence. These include behavioral skills training, medication adherence training, phone reminders, text reminders, smart pill caps, and various combinations thereof. Karters and colleagues systematically reviewed 85 medication adherence trials comprising 16,271 participants and after conducting a network meta-analysis concluded, "Several interventions can improve adherence and viral suppression; generally, their estimated effects were modest and waned over time."¹⁵ The usual methods for monitoring adherence in clinical trials are self-reported medication adherence, pharmacy refill data, Medication Event Monitoring Systems, and therapeutic drug monitoring. Each of these methods has its strengths and weaknesses; but none can be considered a gold standard because of their inherent limitations. Direct observation could be the gold standard, but it is prohibitively expensive and impractical.

Directly observed therapy could be a solution. Directly observed therapy is a means of encouraging strict medication adherence in which a health-care worker or other competent individual physically watches a patient consume their medication. Given the importance of strict medication adherence in HIV/AIDS, there have been efforts to institute directly observed therapy adherence measures.^{16,17} A systematic review and meta-analysis showed that directly-observed therapy of ART "had a significant effect on virologic, immunologic, and adherence outcomes."¹⁸ In-person, directly observed therapy has its critics, however. They suggest it is coercive, dehumanizing, and hinders autonomy.¹⁹⁻²¹

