5.5 STRATEGIES FOR RECRUITMENT AND RETENTION

The target sample will approximate the distribution of HIV/AIDS patients by race and ethnicity, and will equally enroll men and women, as seen in Figure 3.

Figure 3. Target sample by gender, race, and ethnicity.

| Racial Categories | Ethnic Categories | | | | Total | |
|--|------------------------|----------|--------------------|----------|-----------|--|
| | Not Hispanic or Latino | | Hispanic or Latino | | | |
| | Female | Male | Female | Male | | |
| American Indian/ Alaska Native | 0 | 0 | 0 | 0 | 0 | |
| Asian | 0 | 0 | 0 | 0 | 0 | |
| Native Hawaiian or Other Pacific Islander | 0 | 0 | 0 | 0 | 0 | |
| Black or African American | 5 | 5 | 0 | 0 | 10 | |
| White | 4 | 4 | 3 | 3 | 14 | |
| More than One Race | 0 | 0 | 0 | 0 | 0 | |
| Total | 9 | 9 | 3 | 3 | 24 | |

Participants will be recruited from the outpatient population of HIV/AIDS patients in the San Francisco Bay region of California; the study will not enroll participants outside of the United States. Potential participants will be recruited using a 1-page flyer that will be posted in one or more medical practices in the Bay Area that specialize in the prevention and treatment of HIV/AIDS; providers and staff of these practices are not otherwise affiliated with the study.

It is expected that approximately 75% of screened patients will be determined eligible for study enrollment, so approximately 32 individuals will be screened to reach the target sample size (n=24), which we expect to occur at a rate of approximately 2 participants per week.

To aid retention efforts, medication adherence for each participant is monitored through the HiDO platform. The HiDO unit is first and foremost a medication adherence device. The device will transmit real time data about adherence and trial participation. To maintain study integrity, we cannot intervene to promote adherence beyond the reminders and prompts provided by the medication adherence system. That said, having the device in the home is a powerful, indirect participant retention tool.

To compensate participants for their time, participants will receive \$100 gift card, which is disbursed upon return of the HiDO device. Participants who do not complete study receive \$5 for each full week

from device setup to date of notification by either party of study withdrawal, delivered by Visa gift card at device pickup.

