7.3 LOST TO FOLLOW-UP

A participant will be considered lost to follow-up if he or she does not complete the post-intervention interview and questionnaire and is unable to be contacted by the study site staff.

The following actions must be taken if an enrolled participant does not complete the post-intervention interview and questionnaire:

- The site will attempt to contact the participant to determine the cause of the missed interview, and ascertain if the participant wishes to and/or should continue in the study.
- Before a participant is deemed lost to follow-up, the investigator or designee will make every effort to regain contact with the participant (where possible, 3 telephone calls and, if necessary, a certified letter to the participant's last known mailing address or local equivalent methods). These contact attempts will be documented in the participant's study file.

- Should the participant continue to be unreachable, he or she will be considered to have withdrawn from the study with a primary reason of lost to follow-up.

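### Section 4.2 scores withdrawers only up to their exit and leaves other stoppers without a scoring rule, so the 90-day mean adherence can turn on undefined choices

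*Combined protocol and SAP*

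**What the plan says.** Section 3 defines the primary endpoint as "Mean adherence rate to ART in all patients across 90 days". The printed numerator is "n. of doses provided — n. of doses taken", divided by doses provided. Read literally this gives the percentage missed; the evident intent is doses taken over doses provided. Doses provided is not defined as scheduled, loaded or dispensed.

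The only scoring rule for people who stop early is in Section 4.2: "For participants who completely withdraw from the study before 90 days, adherence percentage will only be calculated for the time that they participated". The next sentence adds that "these dropouts will not affect our primary endpoint calculation".

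Two other kinds of stopper appear elsewhere:

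- Section 7.1: "Discontinuation from HiDO platform use does not mean discontinuation from the study, and remaining study procedures should be completed". No section says how that person's remaining days are scored.
- Section 7.3: loss to follow-up is triggered by a missed post-intervention interview (Day 97 ± 7 in Section 1.3) plus failed contact. The participant then "he or she will be considered to have withdrawn from the study with a primary reason of lost to follow-up". No effective date is given.

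Section 9.3 defines a modified intention-to-treat set (at least 7 days enrolled) and a per-protocol set (90 days plus interview and questionnaire). Neither is named as primary. Section 9.1 sets the null below 94% and the alternative at 95% or more. Section 9.4.2 decides between them on descriptive statistics. No sensitivity analysis is planned.

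**The concern.** A rate cut off at withdrawal is not a 90-day rate. A participant who leaves at Day 30 contributes a 30-day percentage with the same weight as a completer's 90-day percentage, so early days count for more than their share. That does no harm if adherence is flat. If it falls over time, the computed mean is too high even when leavers and stayers behave identically. Section 2.1 reports of adherence interventions in general that "their estimated effects were modest and waned over time".

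The second problem is that the cut-off applies only to complete withdrawal. How a stop is classified, and on what date, may then change the score for the same dosing. Section 7.2 lets the investigator withdraw a participant for significant non-compliance, and Sections 2.2 and 5.5 say adherence can be seen in real time. The cut-off date can therefore depend on the outcome being measured.

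At stake is whether Hypothesis 1 is declared met. The hypotheses are one point apart, and Section 9.2 expects only 60% completion.

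**Working it through.** **Plan's own figure.** Section 9.2 wants at least 15 completers at 60% completion from 24 recruited. 15 / 0.60 = 25 and 24 × 0.60 = 14.4, so the stated 24 is reproduced to within one participant. Up to 24 − 15 = 9 may leave early. The documents give no SD, alpha or power.

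**Weight of each period** (mean of participant rates; 15 completers, 9 withdrawers; once-daily dosing assumed).

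- All 9 leave at Day 30: Days 1–30 carry (15 × 30/90 + 9 × 1) / 24 = 14/24 = 58.3% of the weight, and Days 61–90 carry (15 × 30/90) / 24 = 20.8%.
- Exits spread evenly (Days 9, 18, …, 81): 47.2% and 22.8%.
- A true 90-day mean gives each 30-day block 33.3%.

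**Effect if adherence wanes.** Assumptions: the same straight-line decline from a to b for everyone; 40% leave, uniformly over Days 7 to 90 (mean exit day 48.5).

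- True mean: (a + b)/2.
- Mean truncated rate of leavers: a − (a − b) × 48.5/180.
- 99% to 89%: true 94.0; leavers 99 − 10 × 0.2694 = 96.31; computed 0.6 × 94.0 + 0.4 × 96.31 = 94.92.
- 100% to 88%: true 94.0; leavers 100 − 12 × 0.2694 = 96.77; computed 0.6 × 94.0 + 0.4 × 96.77 = 95.11.

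The overstatement is (share leaving) × (a − b) × (0.5 − 0.2694). If only 20% leave early, the second case gives 0.2 × 12 × 0.2306 = 0.55, so 94.55 rather than 95.11.

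A different assumed pattern, 98/95/90% by month, has a true mean of 94.3%. With 15 completers and 9 leavers it is computed as (15 × 94.33 + 9 × 98)/24 = 95.7% if all leave at Day 30, or 95.3% if exits are spread. Pooling doses instead of averaging participants gives 94.9% and 94.8%.

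**Effect of how a stop is classified.** Assumptions: 97% adherence for 30 days, then no doses; doses provided taken as doses scheduled.

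- Cut off at Day 30: 97%.
- Scored to Day 90: 97 × 30/90 = 32.3%.
- Difference in a 24-person mean: (97 − 32.3)/24 = 2.7 points per person. With all 24 at 97% while on the device, reclassifying one takes the mean from 97.0% to 94.3%.

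If doses provided means doses dispensed, both scores are 97% and the gap vanishes. Scheduled doses that were never dispensed then drop out of the calculation, which inflates every stopper's score.

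**The case against.** Several stronger readings are tempting, and the documents do not support them.

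- *A reader might infer that silent stoppers are scored over the full 90 days.* Nothing says so. Section 7.3 deems them withdrawn without a date, so the Section 4.2 cut-off could be back-dated to the last dose. What stands is an undefined rule, not a stated asymmetry.
- *A reader might infer that either party sets the cut-off by giving notice.* The phrase "from device setup to date of notification by either party of study withdrawal" in Section 5.5 governs the gift-card payment only.
- *A reader might conclude that the primary figure is biased upward whatever is done.* The sentence on dropouts in Section 4.2 can be read as leaving them out, and the per-protocol set excludes them. Over-weighting then does not arise. But that figure describes completers, not all patients as Section 3 promises.
- *A reader might apply the classification effect to a mean of 15.* Fifteen is the number of completers sought, and neither a withdrawer nor a silent stopper who misses the interview belongs in the per-protocol set. Only the 24-person figure fits.

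The truncation examples are also fair game. Completion under Section 4.4 includes the last scheduled procedure, so some non-completers may have full 90-day logs and 40% may overstate early leaving. The first example stays between the two hypotheses, and the second crosses 95% by only 0.11 point. The waning statement concerns adherence interventions at large, and Section 2.1 discusses directly observed therapy separately.

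Finally, counting unrecorded doses as missed is not a measure of adherence to ART, because pills can be taken from the device by hand (Sections 2.2 and 2.3.3). That stands, and limits such a figure to a lower bound.

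**Conclusion.** The point holds as a defect of definition, with a possible upward bias. Section 4.2 contradicts itself on whether withdrawers enter the primary figure. If they do, the mean over-weights early weeks: under the stated linear-decline assumptions the overstatement is 0.9 to 1.1 points, and about half that if 20% rather than 40% leave early. If adherence does not wane and leavers resemble stayers, there is no such bias. Scoring after device discontinuation and the end date for loss to follow-up are missing. With scheduled doses as the denominator, that gap is worth 2.7 points per person stopping at Day 30 in a mean of 24; with dispensed doses the gap is nil but stoppers' scores are inflated.

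The stop days, the 97% and the decline shapes are assumptions, not plan figures. For a descriptive single-arm pilot this is a should-fix. It matters because either choice can by itself carry the result across 95%, and no planned analysis would show that it had.

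**What to change.** Amend Sections 3, 4.2 and 9.4.2, before the primary figure is computed:

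1. Define the denominator as doses scheduled, and correct the formula to doses taken over doses scheduled.
2. Apply one end-of-observation rule, dated by the last device interaction, to notified withdrawal, device discontinuation and loss to follow-up alike.
3. Name the analysis set for the primary figure, and remove or reconcile the sentence saying dropouts do not affect it.
4. Compute adherence by study week and average the weekly group means, leaving out a participant's weeks after the end of observation. If leavers and stayers behave alike, this recovers the 90-day mean.
5. Report beside it a lower bound in which every scheduled dose from the end of observation through Day 90 counts as not observed taken. Label it device-confirmed adherence, and print the percentage still using the device at Day 90.
6. Claim that Hypothesis 1 is met over 90 days in all patients only if both figures reach 95%. Otherwise limit the claim to adherence while using the device.

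The cost is a few sentences, using data the device already logs. The downside is a less favourable second figure. With 97% on-device adherence and 9 of 24 stopping at Day 30, the lower bound is (15 × 97 + 9 × 32.3)/24 = 72.8%, and with stops at Day 60 it is 84.9%. If the expected 40% non-completion is mostly early device stopping, the wider claim would not be available.
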